18.9 Adverse Event Collection Timeframe

AEs will be collected and evaluated from the time the informed consent is signed through the EoT. After the EoT and up to the last observation in the study, new AEs will be collected only if deemed related to the study drug, if they are SAEs, or if they are related to a fungal infection.

All AEs reported by the subject or observed by members of the clinical staff will be evaluated by the principal investigator (PI) or qualified designee. The PI will attempt, if possible, to establish a diagnosis based on presenting signs and symptoms. The nature of the AE, time of onset relative to study drug administration, duration, severity, and relationship to treatment should be determined. Details of any corrective treatment must be recorded in the eCRF. The PI will determine whether any changes have occurred in baseline signs and symptoms. All AEs and SAEs will be collected in the eCRF.

18.10 Serious Adverse Event Reporting Requirements

All SAEs must be reported within 24 hours of the site becoming aware of the SAE. Any event that is serious, study drug-related, and unexpected as assessed by the medical monitor or the Sponsor will be submitted to the regulatory authorities in accordance with national regulatory laws and regulations. The PI will be responsible for reporting all SAEs that require reporting to the local Institutional Review Board/Ethics Committee (IRB/EC) in accordance with its regulations and guidelines.

18.11 Adverse Event and Serious Adverse Event Follow-up

All AEs and SAEs will be followed up to resolution (the subject's health has returned to her baseline status or all variables have returned to normal) or until an outcome is reached, stabilization occurs (the investigator does not expect any further improvement or worsening of the event) or the event is otherwise explained, regardless of whether the subject is still participating in the study. All appropriate therapeutic measures should be undertaken and recorded. Where appropriate, medical tests and examinations will be performed to document resolution of the event(s).

18.12 Serious Adverse Event Reporting – Procedures for Investigators

Initial Reports and Follow-Up SAE Reports:

To report an SAE, the SAE eCRF form within the Electronic Data Capture (EDC) system must be completed. All SAEs, whether or not deemed drug-related or expected, must be reported by the investigator or qualified designee within 24 hours of first becoming aware of the event. The investigator/qualified designee will enter the required information regarding the SAE into the appropriate form, which will automatically result in distribution of the information to the appropriate Sponsor contact.

18.13 Procedures for Emergency Unblinding

This is an open-label study. No procedures for emergency unblinding are needed.

19.0 Data Collection, Study Monitoring and Record Management

19.1 Data Collection and Reporting

Data for this study will be collected using eCRFs. The investigator and study site staff will receive training regarding the completion of the eCRF. Visit-specific data should be entered into the eCRF and be ready for review as soon as possible, but no later than 5 days after each visit/time point.

All protocol-required information collected during the study must be entered by the investigator or designated representative in the source documents and eCRF. All data entry, modification or deletion will be recorded indicating the individual subject, original value, the new value, the reason for change, who made the change, and when the change was made. All data changes will be clearly indicated with a means to locate prior values. The investigator will maintain a list of individuals who are authorized to enter or correct data on the eCRFs.

The investigator or designated sub-investigator, following review of the data in the eCRF, will confirm the validity of each subject's data by signing the eCRF.

19.2 Study Monitoring

Study progress will be monitored by the Sponsor or its representative as frequently as necessary to ensure adequate and accurate data collection, protocol compliance, and study conduct in accordance with accepted regulatory requirements. The PI must make all the subject data available to the monitor for review during the planned site monitoring visits. Arrangements for monitoring visits will be made in advance, except in emergency cases.

19.3 Investigator Study Files

The PI is responsible for maintaining all study-related documents in study files. The Sponsor will notify the PI when retention of study files is no longer necessary. The following documents will be kept in the study files or be readily accessible:

- original protocol and all amendments;
- signed agreement or protocol;
- signed and dated study staff roles and responsibilities log;
- copy of the current *curriculum vitae* of the PI and of all sub-investigators;

- IRB/EC membership list and all IRB/EC approvals for the protocol and amendments, informed consent documentation and all updates, advertisements, and written information provided to subjects; all IRB/EC correspondence; documentation that the IB and subsequent revisions have been submitted to the IRB/EC; documentation that all SAEs and any periodic safety reports have been submitted to the IRB/EC; and annual IRB/EC renewals (as required);
- updated laboratory certification and the laboratory's normal values (covering the entire time interval of the study for all laboratory tests conducted during the study);
- all confirmations of investigational drug receipt, drug accountability logs and drug return records;
- a CD or DVD containing final subject eCRF data;
- all correspondence to or from the Sponsor or its designees;
- blank informed consent form;
- Investigator's Brochure;
- subject screening log;
- subject list (contains subject initials and/or protocol-specific subject number);
- all subjects' original signed informed consents; and,
- monitoring visit log.

19.4 Retention of Records

Essential documents should be retained until at least 2 years after the last approval of a marketing application and until there are no pending or contemplated marketing applications, or at least 2 years have elapsed since the formal discontinuation of the clinical development of the investigational product. These documents should be retained for a longer period, however, if required by the applicable regulatory requirements or by an agreement with the Sponsor.

The Sponsor will inform the PI/institution in writing of the need for record retention and will notify the PI/institution in writing when the trial-related records are no longer needed.

An investigator who withdraws from the responsibility of maintaining study records or wishes to move them to a new location has the obligation to place them in safekeeping and to inform the Sponsor of their location.

20.0 Analytical Plan

All statistical processing will be performed using SAS[®] version 9.3 or later, unless otherwise stated.

Descriptive statistics (i.e., number of subjects, mean, standard deviation, median, minimum, maximum) will be presented for all continuous variables; number and

percentage of subjects will be presented for categorical variables. For parameters measured over time, observed data and changes from baseline will be described for each time point.

All analyses of the study results for SCY-078 will be descriptive. Unless otherwise stated, data will be analyzed as is with no imputation.

A Statistical Analysis Plan (SAP) describing all statistical analyses in detail will be provided as a separate document.

20.1 Sample Size Determination

This is an exploratory study and no formal sample size calculation was performed.

A total of 30 subjects are estimated to be adequate for an assessment of the safety and tolerability of SCY-078 in subjects with candidiasis, including candidemia, caused by C. *auris*.

20.2 Analysis Populations

Intent-to-Treat (ITT) Population: The ITT Population will include all subjects who are enrolled in the study.

Per-Protocol (PP) Population: The PP Population will include all ITT subjects who receive at least 10 total days of antifungal therapy (SCY-078), who have an EoT assessment and who have no major protocol violations that would impact the assessment of efficacy.

Safety Population: The Safety Population will include all subjects who receive at least one dose of study medication and have at least one safety assessment post baseline.

PK Population: The PK Population will include all enrolled subjects who provide at least one PK sample.

20.3 Subject Disposition, Discontinuation, and Baseline Data

Subject disposition in terms of the number and percentage of subjects enrolled by site will be tabulated. The number of subjects enrolled, number completing the study and reasons for discontinuation will be summarized. Subject demographics and baseline characteristics such as age, race, ethnicity, sex, weight, height, body mass index, country and other relevant parameters will be tabulated.

Baseline is defined as the last non-missing assessment prior to the date (and time if appropriate) of the first dose of study drug. Change from baseline is defined as:post-baseline value – baseline value.

20.6 Pharmacokinetics (PK Subset Only)

20.6.1 Pharmacokinetic Assessments

PK testing will be conducted for subjects who give their consent to participate in the PK portion of the study (the PK Subset). Up to three (3) blood samples will be collected at the following visits and sampling windows: Treatment Day 2 (one sample collected anytime post dosing), Treatment Days 3 to 5 (one sample collected predose on any of these days), and Treatment Days 7 to 10 (one sample collected predose on any of these days).

20.6.2 Pharmacokinetic Analyses

The PK analysis will be conducted on the PK Population. The concentration versus time data from the sparse PK samples collected in this study will be analyzed using a Pop PK model to estimate C_{max} , AUC and CL/F, as applicable. Further analysis of possible metabolites may be performed.

20.7 Efficacy

20.7.1 Efficacy Assessments

20.7.1.1 Clinical, Mycological and Global Outcomes

Efficacy will be assessed primarily in terms of global success (defined as a complete or partial global (clinical and mycological) response) at EoT as determined by the DMC. Complete global response, partial global response, stable disease and progressive disease at EoT as determined by the DMC will be assessed as exploratory endpoints. Global success, clinical success and mycological success at EoT as determined by the investigator will also be assessed as exploratory endpoints.

Global Outcome

Global outcome will be scored as global success (complete global response or partial global response) or global failure (stable disease or progressive disease)

Global success: Global success is defined as a complete global response or a partial global response

- Complete global response is defined as a complete clinical response (the resolution of all clinical signs and symptoms and/or radiological abnormalities from baseline attributable to the *Candida auris* infection) and a mycological response (mycological clearance (direct and/or negative cultures [when obtainable] and/or normal serological results [when appropriate])
- Partial global response is defined as a partial clinical response (major improvement of all clinical signs and symptoms and/or radiological abnormalities from baseline attributable to the *Candida auris* infection) and a mycological response (mycological clearance (direct and/or negative cultures [when obtainable] and/or normal serological results [when appropriate])

Global failure: Global failure is defined as either stable disease and/or progressive disease

- Stable disease is defined as minor or no clinical improvement but without deterioration and/or unchanged serological response.
- Progressive disease is defined as clinical deterioration necessitating alternative antifungal therapy or resulting in death, and/or worsened serological response, and/or persistence of fungal infection on the basis of culture, microscopic evaluation, or histopathological testing.

Clinical Outcome

Clinical success: clinical success is defined as a complete clinical response (the resolution of all clinical signs and symptoms and/or radiological abnormalities from baseline attributable to the *Candida auris* infection) or a partial clinical response (major improvement of all clinical signs and symptoms and/or radiological abnormalities from baseline attributable to the *Candida* auris infection).

Mycological Outcome

Mycological success: mycological success is defined as a mycological response (mycological clearance (direct and/or negative cultures [when obtainable] and/or normal serological results [when appropriate]).

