9.0 Background Information and Scientific Rationale

9.1 Background Information

Candida is among the most common causes of healthcare-associated bloodstream infections in the United States (US), with an estimate of 46,000 healthcare-associated *Candida* infections occurring among hospitalized patients in the US each year. The CDC surveillance data have reported that approximately 7% of all *Candida* bloodstream isolates tested are resistant to fluconazole and some *Candida* strains are increasingly resistant to first-line and second-line antifungal treatment agents, including azoles and echinocandins.¹ Centers specialized in the treatment of immune-compromised patients report increased frequency of non-*albicans* species of *Candida* with higher incidence of resistance. For example, in a survey conducted in the MD Anderson Cancer Center, Houston, Texas, US (2005–2013), out of 146 isolates of *C. glabrata* evaluated, 30 (20.5%) were resistant to fluconazole; 15 (10.3%), to caspofungin; and 10 (6.8%), to multiple drugs.² Roughly, 30% of patients with drug-resistant *Candida* bloodstream infections (candidemia) due to drug-resistant *Candida* die during their hospitalization.

Candida auris is an emerging fungus that presents a serious global health threat. Healthcare facilities in several countries have reported that *C. auris* has caused severe illness in hospitalized patients. Some strains of *Candida auris* are resistant to all three major classes of antifungal drugs. This type of multidrug resistance has not been seen before in other species of *Candida*. Also of concern, *C. auris* can persist on surfaces in healthcare environments and spread between patients in healthcare facilities, unlike most other *Candida* species.³

SCY-078 is a member of a new class of antifungal agents and is an orally active, semi-synthetic, triterpene derivative of the natural product enfumafungin. SCY-078 is a structurally distinct class of glucan synthase inhibitor that inhibits the synthesis of the fungal cell wall polymer β -(1,3)-D-glucan. Time kill studies have demonstrated that SCY-078 has fungicidal *in vitro* activity against *Candida* spp. isolates similar to that observed with the echinocandins.

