9.2 Rationale for the Study

This study is being conducted to evaluate the efficacy, safety, tolerability and PK (for a subset of subjects) of SCY-078 in male and female subjects \geq 18 years of age with a documented *Candida auris* infection.

The primary efficacy endpoint of the study is global success, defined as either a complete or partial global (clinical and mycological) response. The primary endpoint will be determined at the end of treatment (EoT).^{12,13} Clinical response will be evaluated by the signs and symptoms of the infection and/or imaging scans, if applicable. Mycological response will be assessed by fungal culture and serological testing (β -(1,3)-D-glucan),¹⁴ if applicable. Recurrence will be assessed 42 days after the EoT (Week 6 Follow-up) as a secondary efficacy endpoint. Recurrence is defined as global success at EoT but re-emergence of the baseline *Candida* infection (with the same *Candida* species and involving the same site) during the post treatment follow-up.¹³

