16.10 Mycological Testing

Blood cultures: Two sets of blood cultures will be collected at Screening/Treatment Day 1 (prior to study treatment) and repeated daily or every other day until blood cultures are negative for at least 48 hours (if it is only possible to obtain 1 set of blood cultures, a reason should be documented). Blood should be drawn peripherally [directly from a vein]; however, if this is not possible, blood may be drawn from a central IV catheter. Follow-up cultures will be performed as clinically indicated.

Non-blood cultures: A documented culture positive for *C. auris* of a sample obtained within the last 7 days must be available at Screening/Treatment Day 1 (prior to study treatment). Follow-up cultures from subjects who have non-blood *Candida auris* infections should be performed as clinically indicated.

The study site's local microbiology laboratory will perform identification and *in vitro* susceptibility testing as per their local standards. The investigator should ensure that all *Candida auris* isolates obtained from all cultures performed during the study period are sent to the central microbiology laboratory, as described in the laboratory manual.

Further evaluation to identify the potential mechanism of resistance may be performed. Isolates may be maintained in a repository for potential future use, for subjects that provide consent for future use.

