16.12 Serological Testing

The following serological examinations will be performed at Screening/Treatment Day 1 (prior to study treatment) and at the recommended time points below:

• Two β-(1,3)-D-glucan consecutive tests every 72 hours until negative

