7.1 Primary Endpoint

The primary efficacy objective is to evaluate the efficacy of ibrexafungerp as determined by a DRC by assessing global success (composite assessment of clinical and mycological success) at EoT. The primary efficacy endpoint of the study is the percentage of subjects with global success (complete or partial global response) at EoT as determined by the DRC. Global outcome will be scored as global success (complete global response or partial global response) or global failure (stable disease or progressive disease) or Unable to determine – due to missing data.

Global Response	Outcome Criteria
Success	Complete Global Response: Complete clinical response (the
	resolution of all clinical signs and symptoms and/or radiological
	abnormalities from baseline attributable to the Candida auris
	infection) and a mycological response (mycological clearance
	(direct and/or negative cultures [when obtainable] and/or normal
	serological results [when appropriate])
	Partial Global Response: Partial clinical response (major
	improvement of all clinical signs and symptoms and/or
	radiological abnormalities from baseline attributable to the
	Candida auris infection) and a mycological response
	(mycological clearance (direct and/or negative cultures [when
	obtainable] and/or normal serological results [when appropriate])
Failure	Stable Disease: Minor or no clinical improvement but without
	deterioration and/or unchanged serological response.
	Progressive Disease: Clinical deterioration necessitating
	alternative antifungal therapy or resulting in death, and/or
	worsened serological response, and/or persistence of fungal
	infection on the basis of culture, microscopic evaluation, or
	histopathological testing.
^a Not Evaluable	Outcome cannot be assessed due to missing data

^aCategory added for non-evaluable subjects due to missing data

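### Mycological clearance in the primary endpoint can rest on a normal β-(1,3)-D-glucan alone, a marker tied to the study drug's own target, and no planned analysis shows how many successes do so

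*Protocol*

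**What the plan says.** Protocol 20.7.1.1 makes mycological response a required part of both complete and partial global response, and so of the primary endpoint. It describes that part as "a mycological response (mycological clearance (direct and/or negative cultures [when obtainable] and/or normal serological results [when appropriate". Investigator- and committee-assessed mycological success use the same terms. SAP 7.1 and 7.3.2 carry the definition over unchanged, including "obtainable] and/or normal serological results [when appropriate". Neither document defines when a culture is obtainable or when serology is appropriate.

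Protocol 9.2 states: "Mycological response will be assessed by fungal culture and serological testing", and names β-(1,3)-D-glucan as the serological test. Section 16.12 lists that test only, at baseline and then as "consecutive tests every 72 hours until negative". Section 9.1 describes the drug as a "glucan synthase inhibitor that inhibits the synthesis of the fungal cell wall polymer" β-(1,3)-D-glucan.

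On sampling, Protocol 16.10 says follow-up cultures for non-blood *C. auris* "infections should be performed as clinically indicated". In Table 1 of both documents, serology is a fixed item at EoT (window 2 days either side), while mycological testing at EoT is marked only as if applicable.

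**The concern.** Three features combine.

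- The wording lets serology satisfy the mycological component without a negative culture.
- The schedule makes serology the test more reliably available at EoT.
- The marker is the product of the enzyme the drug inhibits, and it is measured at or close to the last dose.

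A normal glucan at that moment could mean the fungus is gone. In principle it could also mean that surviving fungus is producing less glucan. The serological terms in the failure categories (unchanged for stable disease, worsened for progressive disease) rely on the same marker.

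What is at stake is how to read the headline rate. The study is single-arm, so no control group can separate a pharmacological fall in glucan from clearance. If such an effect exists, within this arm it would add successes rather than remove them. No planned output shows how many successes depend on serology alone.

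**Working it through.** The plan gives no sample-size derivation, threshold or assumed response rate, so there is no stated figure to reproduce. The check is of the text first, then of scale.

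**Text**

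1. Target and marker are the same molecule: Protocol 9.1 against 9.2 and 16.12. Confirmed.
2. Serology can meet the mycological component without culture: the and/or in Protocol 20.7.1.1 and SAP 7.1 and 7.3.2. Confirmed on a literal reading.
3. The route is open in practice: serology is fixed at EoT, culture is conditional (Table 1), and non-blood follow-up culture is at clinical discretion (16.10). SAP 7.3.1 expects pulmonary, intra-abdominal, soft-tissue, bone and joint, and urinary infections, so non-blood disease is anticipated.
4. Limits already in the plan: serology alone never gives global success, because a complete or partial clinical response is also needed. Persistence on culture, microscopy or histopathology is progressive disease and hence failure, if a sample is taken. In candidemia, blood cultures are repeated until negative for at least 48 hours.
5. Neither document restricts how an on-drug glucan may be used, and neither plans an analysis by the basis of mycological response.

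Items 3 and 4 together place the exposure mainly in non-blood infection with clinical improvement and no follow-up culture.

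**Scale**

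Inputs: n = 30 (planned enrolment, Protocol 12.4 and SAP 3.1) and the Clopper-Pearson 95% interval (SAP 7.1.1). The success count of 18 and the number k resting on serology alone are assumptions, not document figures. All 30 subjects are taken as evaluable.

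Each serology-only success contributes 1/30 = 3.3 points. With y = 18 − k, the rate is y/30. The lower limit is the 0.025 quantile of Beta(y, 31 − y), and the upper limit is the 0.975 quantile of Beta(y + 1, 30 − y).

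| Serology-only k | Successes with culture or direct support | Rate | Exact 95% CI |
|---|---|---|---|
| 0 | 18/30 | 60.0% | 40.6 to 77.3 |
| 1 | 17/30 | 56.7% | 37.4 to 74.5 |
| 3 | 15/30 | 50.0% | 31.3 to 68.7 |
| 6 | 12/30 | 40.0% | 22.7 to 59.4 |

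**Denominator**

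SAP 7.1.1 leaves not-evaluable subjects out of the analysis. If the six were reclassified as not evaluable, the rate would be 12/(30 − 6) = 12/24 = 50%, not 40%. A sensitivity analysis has to state which rule it uses.

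**The case against.** The strongest objection is that the decisive step is not in the documents. They say the drug inhibits glucan synthesis. They do not say that circulating glucan falls while viable fungus survives, and they give no serum kinetics. Protocol 9.1 reports fungicidal activity in vitro, which does not suggest living fungus that merely makes less glucan. This stands. A reader might infer that normalisation on this drug does reflect its mechanism, but the documents support only the statement that it might.

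Second, the safeguards listed above narrow the exposed group, possibly to very few subjects or none. Recurrence at Week 6, off drug, may also reveal suppression mistaken for clearance. This stands in large part. However, recurrence is a secondary endpoint that does not correct the primary one, and Week 6 culture and serology are themselves done only if applicable. The committee's charter is not among the documents and may contain guidance, so its absence cannot be asserted.

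Third, Protocol 9.1 says echinocandins share a similar mechanism. Protocol 12.1 plans a comparison with historical patients on standard care. If those include echinocandin-treated patients whose outcome used the same marker, they may be affected too. A reader might infer a bias in favour of the study drug in that comparison, but its direction cannot be determined from the documents.

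Fourth, the underlying gap, optional culture with serology as a substitute, would exist for any marker. That is true. The link to the drug's target is a further reason to make the dependence visible.

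**Conclusion.** The point holds in a limited form. As written, a subject can be a primary-endpoint success with a normal on-drug glucan as the only mycological evidence. That marker is tied to the drug's target, so it may be weaker evidence than a negative culture. Whether this misclassifies anyone, and how often, is unknown from the documents.

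The size is 3.3 points per serology-only success at n = 30. The 60% against 40% comparison rests on assumed counts and should not be read as an upper bound, because nothing in the plan caps the number at six. For a given k, the overstatement lies between 0 and k/30, depending on how many of those subjects were truly cleared.

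A reader might also conclude that the primary definition must be rewritten to require culture. The documents do not compel that. Some sites cannot be resampled. The SAP was also written late (it already reports that PK samples could not be analysed), so redefining the primary endpoint of an open-label study at that stage would raise its own questions. The warranted change is transparency at low cost.

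**What to change.** Leave the primary definition unchanged, and make three additions.

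- **Committee form:** the review committee (DMC in the protocol, DRC in the SAP) records the basis of each mycological response as culture or direct examination, culture plus serology, or serology only.
- **SAP 7.1.1:** pre-specify a sensitivity analysis of the primary endpoint in which serology-only responses count as not successful and stay in the denominator, with the same exact interval, shown beside the main result.
- **Listing:** for the serology-only subjects, list any Week 6 off-drug glucan and culture results.

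The cost is one field on the committee form, one extra row in the primary table and one listing. No new test is needed. The drawback is that the sensitivity rate is conservative, because it counts truly cleared subjects whose site could not be resampled as not successful. It should be labelled as a lower bound with respect to serology-only responses, with the main result as the corresponding upper end. If no success rests on serology alone, the two rows agree and the headline result is strengthened.

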7. EFFICACY

The primary efficacy and secondary efficacy endpoints will be performed on the ITT and PP populations. The ITT analyses will be considered primary and the PP analysis will be considered supportive of the primary analyses on the ITT population.

The primary efficacy endpoint of the study is the percentage of subjects who achieve Global Success at EOT, as determined by the DRC. Secondary efficacy endpoints include the percentage of subjects with a recurrence of the baseline fungal infection 42 days after EoT (Week 6 Follow up) as determined by the DRC, and the percentage of subjects surviving 42 and 84 days after Day 1 (first dose of study drug).

Efficacy outcomes will be based on definitions captured in Table 3. Criteria for the Investigator is outlined in Section 7.3.

Additional efficacy endpoints to be evaluated are in Section 7.3.

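### The primary endpoint's written success and failure definitions are neither mutually exclusive nor exhaustive, and the SAP is inconsistent about subjects with complete data who fit neither

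*Protocol*

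**What the plan says.** Protocol 20.7.1.1 sets the score: "Global outcome will be scored as global success (complete global response or partial global response) or global failure (stable disease or progressive disease"). A complete or partial global response requires a complete or partial clinical response together with a mycological response, which is "mycological clearance (direct and/or negative cultures [when obtainable] and/or normal serological results [when appropriate"]).

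The two failure classes have their own limbs. Stable disease "is defined as minor or no clinical improvement but without deterioration and/or unchanged serological response". The clinical limb of progressive disease is "clinical deterioration necessitating alternative antifungal therapy or resulting in death"; the remaining limbs of that class are "and/or worsened serological response, and/or persistence of fungal infection on the basis of culture, microscopic evaluation, or histopathological testing". Because the limbs are joined by and/or, one serology or culture finding is enough for failure.

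The synopsis and the outcome table in SAP 7.1 repeat these definitions (the table again has "worsened serological response, and/or persistence of fungal" infection), and SAP 7.3.2 repeats the definition of mycological success. SAP section 7 relies on them: "Efficacy outcomes will be based on definitions captured in" the outcome table. Protocol 9.2 adds "Mycological response will be assessed by fungal culture and serological testing", where applicable.

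The SAP adds a third outcome. SAP 3.3, 7.1 and 7.3.1 reserve it for missing data. SAP 7.1.1 applies it to any subject not deemed a success or failure, and leaves that subject out of the analysis. Protocol 20.4 counts a subject with no end-of-treatment assessment as a treatment failure.

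**The concern.** A primary endpoint scored as success or failure needs definitions that place each subject with complete data in exactly one class. Here the success limb and the failure limbs were written separately. Nothing says how culture and glucan combine when they disagree, or which limb prevails when both are met. The qualifiers on obtainable cultures and appropriate serology deal with whether a marker is available, not with disagreement between two available markers.

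For the affected subjects the text does not settle whether the primary score is success, failure or exclusion. The choice carries into recurrence, which requires global success at end of treatment (SAP 7.2), and into the response categories, the investigator-scored success and the subgroup tables (SAP 7.3.1).

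**Working it through.** The plan gives no figure to reproduce: both documents state that no formal sample size calculation was made. The check is therefore one of logic.

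**Inputs.** The rules are those of Protocol 20.7.1.1 and the SAP 7.1 table. I crossed:
- 5 clinical states: complete response; major improvement; minor or none; deterioration needing alternative therapy or ending in death; deterioration short of that
- 3 culture states: negative, positive, not obtained
- 4 glucan states: normal; improved but not normal; abnormal and unchanged; worsened

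This gives 5 × 3 × 4 = 60 cells, of which 2 × 3 × 4 = 24 are clinical responders. Cells are combinations of findings, not frequencies.

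**Rules.** Success = clinical response and clearance. Failure = minor or no improvement, or unchanged abnormal glucan, or worsened glucan, or positive culture, or deterioration with alternative therapy or death.

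| Reading of clearance | Meets both | Meets neither |
|---|---|---|
| Any clear marker | 6 (all responders) | 6 (2 responders, 4 deteriorating) |
| Every available marker clear | 0 | 8 (4 responders, 4 deteriorating) |

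- *Overlap, any-marker reading.* Negative culture with unchanged or worsened glucan: 2 clinical levels × 2 = 4. Positive culture with normal glucan: 2 × 1 = 2. Total 6 of 24 responder cells.
- *No class, every-marker reading only.* Responder, negative culture, glucan improved but not normal: 2 cells.
- *No class, either reading.* Responder, no culture, glucan improved but not normal: 2 cells. Deterioration short of alternative therapy or death, culture negative or not obtained, glucan normal or improved: 2 × 2 = 4 cells.

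**Size.** With about 30 subjects planned, one reclassified subject moves the rate by 1/30 = 3.3 points. As an illustration, assume 15 clear successes, 12 clear failures and 3 responders with negative culture and glucan improved but not normal:
- any-marker reading, scored as success: 18/30 = 60.0% (Clopper-Pearson 95% CI 40.6 to 77.3)
- every-marker reading, failure by default: 15/30 = 50.0% (31.3 to 68.7)
- every-marker reading, SAP 7.1.1 taken literally: 15/27 = 55.6% (35.3 to 74.5)

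**Check of the fix.** If a positive culture never counts as clearance, one limb has stated precedence, and every remaining complete-data subject is a failure, no cell meets both classes or neither, on either reading. The two readings then differ only for responders with negative culture and non-normal glucan: 2 × 3 = 6 of 24 cells if success takes precedence, or 2 × 1 = 2 of 24 (improved glucan only) if the failure limbs do.

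**The case against.** The strongest reply is that the overlap needs the less natural reading. The qualifiers on availability, and the joining of the two tests in Protocol 9.2, favour requiring every available marker to be clear, and on that reading the overlap is zero. That is a fair argument, but neither document adopts the reading, and it increases the number of unclassified responder cells from 2 to 4.

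A committee assigns the outcome, and its charter may hold the rule. That stands, so the point is limited to the protocol and SAP text. Blood cultures and glucan are also both repeated until negative (Protocol 16.10 and 16.12), which limits disagreement. Against that, follow-up culture of non-blood infections is only as clinically indicated, and at end of treatment serology is scheduled for all while mycological testing is done if applicable.

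A reader might go further than the text allows in four ways:
- *That the SAP plans to drop complete-data subjects.* This rests on one sentence of SAP 7.1.1; SAP 3.3, 7.1 and 7.3.1 tie the category to missing data. The wording is inconsistent, but an intention to exclude is not shown.
- *That the missing any-or-every rule is the whole cause.* Six cells fit no class whichever rule is chosen.
- *That a glucan normal throughout is a failure because it is literally unchanged.* The same section lists normal serology as clearance, so this is strained; it merits one clarifying clause.
- *That 6 of 24 is a share of patients, or that every ambiguous subject could be a success.* Cells carry no weights, and the four deterioration cells and the two no-culture responder cells are not successes on either reading.

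**Conclusion.** The point holds for the written definitions. They overlap on the any-marker reading, leave gaps on both readings, and state no precedence. The SAP gives inconsistent instructions for complete-data subjects who fall in a gap.

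The number affected cannot be derived from the documents; the 3 subjects and the 15/12 split above are assumptions. What is firm is 3.3 points per reclassified subject at n=30. The study is descriptive with no stated success threshold, so the consequence is for the reported rate, its interval and the outcomes built on it, not for a formal test. It should be corrected, but it does not undermine the design.

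**What to change.** By SAP amendment before database lock and without reference to outcome data, or by citing the committee charter if it already holds the rule:

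1. Reconcile the success and failure limbs. State whether any or every available marker must be clear and which limb prevails when markers disagree; both are the sponsor's choice. State that persistence on culture, microscopy or histopathology is not clearance, and that the unchanged-serology limb does not apply to values normal throughout.
2. Score any subject who has the needed end-of-treatment data and does not meet success as a failure. Amend SAP 7.1.1 so that the not-evaluable category covers missing data only. Reconcile this with Protocol 20.4, which makes a missing end-of-treatment assessment a failure. State how the added failures divide between stable and progressive disease, since SAP 7.3.1 reports each.
3. As a sensitivity analysis, report the primary rate with its Clopper-Pearson interval under the any-marker and the every-available-marker readings, both after items 1 and 2. This is better than scoring all flagged subjects as success and then as failure, because some of them cannot be successes on either reading.

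The cost is an amendment, matching committee wording and two extra rows in the primary table; no new procedure is needed. The headline rate may become slightly less favourable: counting an unclassified subject as a failure instead of excluding that subject cannot raise it.
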